CCMO	Central Committee on Research Involving Human Subjects; in Dutch: Centrale Commissie Mensgebonden Onderzoek
COMPASS	COMparison of Posterolateral and direct Anterior approach in uncemented total hip arthroplasty with a Short Stem prosthesis
CV	Curriculum Vitae
DSMB	Data Safety Monitoring Board
EU	European Union
GCP	Good Clinical Practice
IB	Investigator's Brochure
IC	Informed Consent
IMP	Investigational Medicinal Product
IMPD	Investigational Medicinal Product Dossier
METC	Medical research ethics committee (MREC); in Dutch: medisch ethische toetsing commissie (METC)
(S)AE	(Serious) Adverse Event
SPC	Summary of Product Characteristics (in Dutch: officiële productinformatie IB1-tekst)
Sponsor	The sponsor is the party that commissions the organisation or performance of the research, for example a pharmaceutical company, academic hospital, scientific organisation or investigator. A party that provides funding for a study but does not commission it is not regarded as the sponsor, but referred to as a subsidising party.
SUSAR	Suspected Unexpected Serious Adverse Reaction
Wbp	Personal Data Protection Act (in Dutch: Wet Bescherming Persoonsgegevens)
WMO	Medical Research Involving Human Subjects Act (in Dutch: Wet Medisch-wetenschappelijk Onderzoek met Mensen)
DAA	Direct Anterior Approach
PLA	PosteroLateral Approach
NOV	Nederlandse Orthopaedische Vereniging (Dutch Orthopaedic Society)
MIS	Minimal Invasive Surgery
THA	Total Hip Arthroplasty

NWZ	Noordwest Ziekenhuisgroep(participating hospital)
VAS	Visual Analogue Scale
OHS	Oxford Hip Score
HHS	Harris Hips score
QoL	Quality of Life
EQ-5D	EuroQol 5 Dimensions quality of life test
BMI	Body Mass Index
HOOS	Hip dysfunction and Osteoarthritis Outcome Score
NFU	Dutch Federation of Academic Centers (Nederlandse Federatie van Universitaire centra)
NWZ	Noordwest Ziekenhuisgroep location Alkmaar

SUMMARY

The purpose of this randomized controlled study is to compare posterolateral approach (PLA) and direct anterior approach (DA) in total hip arthroplasty with the NANOS short stem for subsidence, functional outcome, quality of life and isometric hip abduction force over a follow-up period of 2 years.

1 INTRODUCTION AND RATIONALE

Background

Short-stems total hip prostheses, such as the NANOS prosthesis, pose possible advantages for active patients. Because a large part of the column femoris remains intact it is possible to create a more anatomical reconstruction of the hip joint. This leads to better off-set restoration which may improve hip abductor function^{1,2}. A reduced capacity of the abductor muscles might result in aberrant hip abduction/adduction pattern during walking, which might be problematic in for example the regulation of medio-lateral balance during walking. Another advantage in active patients is that the NANOS stem fixates proximally in the femur leaving more bone stock for a possible subsequent revision. Because of the proximal fixation it is suspected that the NANOS causes less stress shielding of the trochanter region³ and flexibility of the femur shaft is left intact leaving a natural capacity to bending forces on the femur shaft

The NANOS prosthesis was developed in 2002. Since its release positive results have been presented (table 1 and table 2) for complication rates and revision rates. Also, an ODEP 3A* rating was assigned in 2016.

Table 1: Summary of results of the NANOS prosthesis

Title/Reference	Author/s	Cases	Survival Rate	Follow-up	Other Relevant Data
Keep it short and simple – Ergebnisse einer Multicenter-Studie. Orthopädie im Profil 1/2007	A. Reinhardt	183	100 %	52 cases 2 years	No complications to date, HHS Preop 47.1, Postop 95.8
5 years clin. experiences of a neck preserving stem. Presentation Smith & Nephew Mediterranean Hip Meeting 2010, Greece	F. Parente	222	100 %	62 cases 3–5 years	No revision, no dislocation was observed in any of the stems
3 to 5 year results of NANOS neck preserving stem. Presentation 58 th Annual VSO Meeting 2010, Germany	P. Ettinger M. Ettinger	68	100 %	68 cases 3–5 years	No revision, no migration was observed in any of the stems, HHS Preop 47.5, Postop 95
NANOS neck preserving stem an alternative system in endoprothetic implantation in younger patients. Presentation 58 th Annual VSO Meeting 2010, Germany	K. Moussa H. Dinges	110	100 %	110 cases 2.5 years	No revision, no radiographic signs of loosening or migration were observed in any of the stems, HHS Preop n/a, Postop 94
Results after implantation of the NANOS neck preserving stem. Presentation 58 th Annual VSO Meeting 2010, Germany	L. Engelmann	50	96 %	50 cases 3–6 years	No radiographic signs of loosening observed in any of the stems. Two joint revisions (cause was not reported). HHS Preop 47.3, Postop 97.8

Table 2 Cumulative Percent Revision of Primary Total Conventional Hip Replacement using a Mini Stem Prosthesis (Primary Diagnosis OA)

Femoral Component	N Revised	N Total	1 Yr	3 Yrs	5 Yrs	7 Yrs	10 Yrs
C.F.P.	9	123	4.1 (1.7, 9.5)	4.1 (1.7, 9.5)	4.9 (2.2, 10.6)	5.8 (2.8, 11.7)	7.9 (4.2, 14.7)
Mallory-Head	3	74	2.8 (0.7, 10.8)	6.3 (1.8, 20.4)			
Mayo	6	96	2.1 (0.5, 8.1)	4.2 (1.6, 10.8)	4.2 (1.6, 10.8)	5.7 (2.4, 13.4)	7.9 (3.5, 17.4)
Metha	4	100	3.3 (1.1, 9.8)	4.6 (1.7, 11.7)			
MiniHip	11	461	2.2 (1.2, 4.3)	3.2 (1.7, 5.8)			
Nanos	5	629	0.7 (0.3, 1.8)	0.9 (0.4, 2.2)			
Silent	2	50	4.0 (1.0, 15.1)	4.0 (1.0, 15.1)			
Taperloc Microplasty	5	230	1.9 (0.7, 5.1)	1.9 (0.7, 5.1)			
Other (2)	2	15	6.7 (1.0, 38.7)	6.7 (1.0, 38.7)	6.7 (1.0, 38.7)	6.7 (1.0, 38.7)	
TOTAL	47	1778					

The use of short stems corresponds with the trend of direct anterior and minimal invasive hip surgery we have seen last years. With these techniques more muscles are left intact and might therefore result in a better functional outcome, leading to shorter operation time, less perioperative complications and less muscle damage⁴. Thus, both the short stem total hip prostheses as well as the direct anterior and minimal invasive approaches in hip surgery can be considered relatively recent innovations in THA and both are aimed at improving functional and clinical outcome, mainly in the short term. However, the clinical and functional effectiveness of the combination, i.e. whether the use of short stem prostheses is even more effective when used during the direct anterior approach compared to when used during the regular posterolateral approach in THA, is as far as we know not yet investigated. Important parameters in THA which may be related to clinical and functional outcome are the level of fixation and positioning of the (short) stem, which are thought to be affected by surgical approach. In literature, it is well established that early migration (migration within two years after THA) of the stem is predictive for late aseptic loosening of the stem^{5,6}. The computer-assisted Einzel-Bild-Roentgen-Analyse (EBRA) system was evaluated to detect stem migration of 1 mm with a specificity of 100% and a sensitivity of 78%⁷. This method is less invasive and easier to use in a clinical setting than the gold standard RSA method. A migration threshold of 1.5 mm after two years was found to be highly predictive for later aseptic loosening and significantly increased risk of revision⁵. Comparing the level of migration of the short stem of the hip prosthesis for the direct anterior approach and the posterolateral approach in THA might add to the knowledge base of the effectiveness of the

direct anterior approach and may help in evidence based clinical decision making when deciding for the best treatment option when a patient's hip needs to be replaced.

2. OBJECTIVES AND HYPOTHESIS

Primary Objective:

The primary objective of this study is to investigate whether the NANOS femoral stem placed by means of the direct anterior approach (DAA) results in a better rigid fixation at two years follow-up in comparison with the NANOS stem placed using the posterolateral approach (PLA) in patients with hip osteoarthritis who need a total hip arthroplasty (THA).. Also, stem position and off-set restoration will be taken into account.

Secondary Objectives:

The secondary objective is to compare THA with the short stem NANOS prosthesis using the DAA with the PLA for perceived pain, functioning of the hip, quality of life, isometric hip abduction force and quality of walking during the first two years after surgery.

Hypotheses:

- The NANOS short stem prosthesis will show less subsidence if placed by means of the DAA compared to the PLA at two years follow-up
- The NANOS short stem prosthesis will show better stem position if placed by means of the DAA compared to the PLA at two years follow-up
- The NANOS short stem prosthesis will show better off-set if placed by means of the DAA compared to the PLA at two years follow-up
- The NANOS short stem prosthesis will show lower pain scores if placed by means of the DAA compared to the PLA
- The NANOS short stem prosthesis will show a better functional outcome and range of motion if placed by means of the DAA compared to the PLA
- The NANOS short stem prosthesis will show higher maximum isometric hip abductor muscle force if placed by means of the DAA compared to the PLA
- The NANOS short stem prosthesis will show a better gait pattern in terms of hip joint angles and hip joint moments in the frontal plain if placed by means of the DAA compared to the PLA

3. STUDY DESIGN

This study will be a single center, randomized controlled clinical trial (RCT). This study contains two arms, one with patients treated by means of the DAA and one with patients treated by means of the PLA.

Two surgeons will be participating in this study. Both are senior hip orthopedic surgeons for the NANOS prosthesis and both orthopedic surgeons will perform the DAA and the PLA. If the indication for primary hip arthroplasty is established, patients will be asked if they want to participate. Patients who are interested in participating will get an appointment with the research nurse after one week. Then informed consent will be signed and patients will be randomized to one of the two study arms. Registry of data and block randomization will be executed via Castor.

As primary outcome we will use the migration of the NANOS prosthesis in mm as measured with EBRA-FCA software. In addition, we will investigate functional outcome and quality of life with the HOOS and EQ-5D questionnaires.

Basic balance and gait performance will be tested using the timed “up & go” (TUG) test, instrumented with inertial sensors to measure body segment accelerations and angles, and a two times 50 meter walk at their preferred walking speed, also instrumented with inertial sensors⁸⁻¹². For the TUG test¹³, in short, participants will be asked to stand up from a chair, walk for 3 meters, walk back to the chair and sit down on the chair. The time needed to perform the TUG test as instructed will be registered. In addition, the participants will wear validated inertial sensors (McRoberts Dynaport Hybrid, Dimensions 87 x 45 x 14 mm, Weight 74 grams)¹⁴, which will be attached to the lower back with Velcro fixation.

The study will take place between 2017 and 2020 in the Noordwest Ziekenhuisgroep location Alkmaar.

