4.4 Sample size calculation

The main hypothesis of this study is that the NANOS short stem prosthesis will show less subsidence if placed by means of the DAA compared to the PLA at two years follow-up. No previous studies have been published in which differences in subsidence between DAA and PLA are compared for short stem prostheses.

The study design of the present study is an RCT. We calculated our sample size based on the study of Budde et al.¹⁵. In this study a mean subsidence of 0.46 ± 0.31 mm was measured for the NANOS stem prosthesis after 2 years of follow-up. When assuming a mean subsidence of 0.46 mm in the PLA group and 0.25 mm less subsidence in the DAA group, a sample size of 25 subjects in each group (a total of 50 subjects) is necessary to detect a difference with a power of 80% and a two-sided 5% significance level using an independent t-test.

Since the follow-up of patients is almost similar to the regular follow-up of patients that undergo total hip replacement, we do not expect a high number of patients that are lost to follow-up. Therefore, we will include 10% more patients, which resulted in 56 patients.

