5. TREATMENT OF SUBJECTS

Two surgeons will be placing the NANOS stems. Both surgeons will use the direct anterior approach (DAA) and the posterolateral approach (PLA). Both surgeons have extensive experience with both these approaches and previous experience with the NANOS stem.

We will use a follow-up protocol that is similar to the NOV (Dutch orthopedic society) THA guidelines¹⁶. This protocol contains postoperative clinical and radiological visits at 8 weeks and one year. In addition, we will send patients functional evaluation questionnaire (HOOS, VAS) at 3 and 6 months. At 24 months we will schedule an additional clinical and radiological follow-up visit.

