Operation parameters such as operation time and blood loss will be registered. During the first 3 days after surgery, on the second postoperative day standing AP radiographs of the pelvis will be made. The two orthopedic surgeons involved in the study have experience with placement of the NANOS stem. Each surgeon performs about 40 to 100 total hip replacements each year. Both surgeons are experienced in performing either the direct anterior approach or the posterolateral approach. The total time of hospital stay will be registered. Complications and adverse events are noted at discharge.

Follow-up assessments

A questionnaire including the HOOS, VAS, EQ-5D and complications has to be completed by the participant at the regular follow-up visits at the orthopaedic outpatient department at 8 weeks (± 14 days) and 12 months (± 31 days). In addition, the participants have to fill in the HOOS, VAS, EQ-5D at 3 and 6 months. The questionnaires will be sent to the patient's home by post or e-mail. Participants will be able to return the questionnaire without making additional costs.

At the regular visit to the orthopaedic outpatient department at 8 weeks, radiographs of the pelvis will be taken according to the standard protocol (standing AP and lateral views) extra attention will be given for correct patient positioning for later migration analysis. At the regular visit to the orthopedic outpatient department at 12 months, balance and gait performance will again be tested using the TUG test and the two times 50 meter walk, both instrumented with inertial sensors. Also at 12 months standardized standing AP radiographs of the pelvis and axial radiographs of the treated hip will be made. One additional clinical radiological follow-up visit will be scheduled 24 months after surgery. At that moment, the participant will be asked to complete the HOOS, VAS and EQ-5D and the stem positioning will be assessed using standing AP pelvis and axial hip x-rays.

Table 1: Overview of the time schedule of the assessment of the study parameters

	1**	2**	3**	4**	5	6	8**	9***
Location	OC*	IC*	IC	OC	Q*	Q	OC	OC
Assessment	Pre-op	Operation	Day 1-3	8 weeks	3 months	6 months	12 months	24 months
Window				± 14 days	± 31 days	± 31 days	± 60 days	± 60 days
Parameter								
Demographic characteristics	X							
Clinical outcome								
HOOS	X			x	x	x	x	x
VAS	X		x	x	x	x	x	x
Hospital stay			x					
EQ-5D	X			x	x	x	x	x
Complications			x	x	x	x	x	x
Functional outcome								

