10. STATISTICAL ANALYSIS

10.1 Primary study parameter(s)

To answer our primary research question, subsidence at two years will be used. Secondary measurements include subsidence at 8 weeks and at 12 months. The EBRA-software needs at least 4 similar radiographs to correctly measure subsidence. The subsidence will be measured in mm with one decimal point behind the comma. In order to determine if there is a difference between the mean amount of subsidence (measured with the EBRA FCA) of the posterolateral and direct anterior approach group an independent t-test will be carried out and the 95% CI for the mean difference will be determined. Pearson's r will be used to calculate the effect size. The assumption of normality will be checked by visual inspection of the q-q plot and the box plot of the data within the groups. A Shapiro-Wilks test will also be performed on the data within the groups. Homogeneity of variance will be checked using the Levene's test.

The effect of time (e.g. at 1 day, 8 weeks, 12 months and 24 months postoperatively) on the amount of subsidence (measured with the EBRA FCA) will be examined with a one-way between subjects ANOVA. Eta^2 will also be calculated to determine the effect size. Tukey's HSD test will be used to identify where the specific differences occurred between the two groups. It is also used to calculate the 95% CI for each difference between the means.

The outcome parameters will be described in terms of means and standard deviations if the data are normally distributed. If the data are not normally distributed then they are described in terms of median, interquartile range and minimum and maximum values. Categorical study parameters are described as proportions.

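### Two surgeons work in both arms, but the protocol states no stratification by surgeon, does not settle the surgeon before open allocation, and fixes a primary t-test without a surgeon term

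*Protocol*

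**What the plan says.** - **Surgeons.** Protocol sections 3 and 5 state that two surgeons take part and that each performs both the DAA and the PLA.
- **Allocation.** Section 3 places consent at a research-nurse appointment, followed by randomisation. The method is given as "Registry of data and block randomization will be executed via Castor". Section 8.2 adds that baseline measurements are registered, that the patient is then randomised, and that neither patient nor surgeon is blinded. Neither section names a stratification factor or says when, or by whom, the operating surgeon is assigned.
- **Primary analysis.** Section 10.1 fixes the test on two-year subsidence: "an independent t-test will be carried out and the 95% CI for the mean difference will be determined". No covariate is mentioned.
- **Sample size.** Section 4.4 rests on the same test, "with a power of 80% and a two-sided 5% significance level using an independent t-test", with inputs "a mean subsidence of 0.46 ± 0.31 mm was measured for the NANOS stem prosthesis after 2 years of follow-up" and "0.25 mm less subsidence in the DAA group". It concludes that "a sample size of 25 subjects in each group (a total of 50 subjects) is necessary", raised to 56 for loss to follow-up.

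**The concern.** The treatment under study is a surgical technique, so the operator is part of how it is delivered and may well influence stem fixation. With two operators, three gaps coincide: no stated stratum, no stated point at which the surgeon is settled, and no surgeon term in the primary test.

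Two different things could follow, and they should be kept apart:

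1. If the surgeon does not depend on the allocation, surgeon shares differ between arms only by chance. That is random error. Leaving surgeon out of the model can cost precision.
2. If the surgeon is chosen once the allocation is known, and in line with it, the comparison of approaches also becomes a comparison of surgeons. Randomisation does not protect against a choice made after it.

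The first is a matter of efficiency. The second could bias the primary estimate, and the protocol has no rule that rules it out.

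**Working it through.** **Inputs from section 4.4:** SD 0.31 mm, target difference 0.25 mm, two-sided 5%, power 80%, 25 per arm, 56 recruited. **Assumed, because the documents give no figure:** a surgeon difference of 0.1 to 0.31 mm (the upper end is one SD), equal caseloads, 0.31 mm as the within-surgeon SD, and any split of surgeons that follows the arm.

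**1. The plan's own figure.** n per arm = 2 × (1.96 + 0.8416)² × 0.31² / 0.25² = 24.1, so 25 per arm and 50 in total. Exact t-test power at 25 per arm is 79.8%. Allowing for 10% loss, 50 / 0.9 = 55.6, so 56. The stated numbers reproduce, with no margin in power.

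**2. Chance imbalance, surgeon independent of arm.** Take 28 patients per arm and 28 per surgeon (hypergeometric). The difference in surgeon share moves in steps of 2/28 = 7.1 points and has an SD of 13.5 points. The chance of a difference of 21.4 points (6/28) or more is 18.1%; of 25 points or more, 6.0%. A 21.4-point imbalance shifts that trial's estimate by 0.214 × 0.1 = 0.02 mm up to 0.214 × 0.31 = 0.07 mm. Over repeated trials the mean shift is zero.

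**3. Precision, surgeon independent of arm.** Without a surgeon term the total SD is √(0.31² + d²/4), where d is the surgeon difference. Power is for 25 per arm:

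| d (mm) | Total SD (mm) | Power, plain t-test | Power with surgeon term (simulated) |
|---|---|---|---|
| 0 | 0.310 | 79.8% | about 79% |
| 0.1 | 0.314 | 78.8% | about 79% |
| 0.2 | 0.326 | 75.8% | about 79% |
| 0.31 | 0.347 | 70.5% | about 79% |

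Simulated type I error of the plain t-test stays at about 5% in every row (20,000 trials each).

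**4. Surgeon chosen in line with the allocation.** Shift = (difference in surgeon share) × d. For illustration, take an assumed split of 80:20 in one arm and 20:80 in the other, so the difference in share is 0.6. There are 25 per arm and no true approach effect:

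| d (mm) | Shift (mm) | Type I error, plain t-test | With surgeon term |
|---|---|---|---|
| 0.1 | 0.6 × 0.1 = 0.06 | about 10% | about 5% |
| 0.2 | 0.6 × 0.2 = 0.12 | about 25% | about 5% |
| 0.31 | 0.6 × 0.31 = 0.19 | about 49% | about 5% |

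An assumed 70:30 split with d = 0.2 mm gives a shift of 0.4 × 0.2 = 0.08 mm and a type I error of about 14%.

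The model term alone does not repair this case fully. With a 0.6 difference in share, approach and surgeon correlate at 0.6. The standard error grows from 0.31 × √(2/25) = 0.088 mm to 0.088 / √(1 − 0.36) = 0.110 mm, and power for 0.25 mm falls to about 60%.

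**5. After the change.** With blocks stratified by surgeon and a surgeon term, simulated power is 79.5% to 80.1% and type I error 4.4% to 4.9% for surgeon differences from 0 to 0.31 mm (N = 50, blocks of 4). Stratifying but keeping the plain t-test makes the test conservative: at 0.31 mm, type I error is 2.5% and power 73%.

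**The case against.** **An unadjusted t-test is valid in a randomised trial.** This stands as long as surgeon is independent of arm. Surgeon is crossed with approach, expected imbalance is zero, and the 18.1% in step 2 is chance error that the confidence interval already covers. Calling it bias would be wrong.

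**The harmful scenario is conjecture.** A reader might infer from the two-surgeon design that approach and surgeon are confounded. The protocol does not support that: nothing says that either surgeon prefers an approach or that cases are booked by arm. Section 4.1 has the surgeon and patient deciding together on uncemented THA, which is an inclusion condition, so a surgeon is involved before allocation. But the text does not say that this surgeon operates. The scenario is therefore neither shown nor excluded.

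**The surgeons are equally qualified.** Section 8.3 says "Both surgeons are experienced in performing either the direct anterior approach or the posterolateral approach", from which a reader might infer that each surgeon masters only one approach. Sections 5 and 5.1 settle this: both have extensive experience with both approaches, and no learning curve is expected. The sentence is loose drafting and carries no weight here. Experience does not guarantee equal subsidence, however, and caseload is not broken down by approach.

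**The gain is small.** True below about 0.2 mm. A difference of 0.31 mm is a full SD and exceeds the treatment target, which is a lot for two senior surgeons using one stem. If 0.31 mm already contains surgeon variation, the loss is smaller still.

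**Strata may be set elsewhere.** Stratification could be configured in Castor, so the fair statement is that none is stated, not that none exists. The t-test, by contrast, is fixed in the protocol, and when the surgeon is settled is a matter of conduct that an analysis plan cannot restore after enrolment.

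**Conclusion.** The point holds as a gap in the design with a cheap remedy, not as a demonstrated flaw. The protocol states no stratification by surgeon, leaves open whether the surgeon is settled before the allocation is known, and fixes a primary test that ignores surgeon.

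If surgeon is independent of arm, there is no bias in expectation and no inflation of type I error. The loss of power is about 1 point at a 0.1 mm surgeon difference, 3 at 0.2 mm and 8 to 9 at 0.31 mm. If the surgeon follows the allocation, the bias equals the difference in surgeon share times the surgeon difference, in a direction that cannot be predicted. The 0.12 mm shift, about half the 0.25 mm target, shows what an 80:20 against 20:80 split and a 0.2 mm difference would do; it is not an estimate for this trial.

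The results with a surgeon term also assume that the surgeon difference is the same under both approaches and that patients are not steered to a surgeon by prognosis.

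**What to change.** 1. **Sections 3 and 8.2:** record the intended operating surgeon before Castor releases the allocation, and stratify the blocks by that surgeon. If strata are already configured, say so.
2. **Section 10.1:** replace the independent t-test by a linear model with approach and surgeon as fixed effects. Report the same contrast, the DAA–PLA mean difference with its 95% CI. Use the surgeon recorded at randomisation, and tabulate the actual operating surgeon by arm.
3. **Make both changes together.** The early record and the strata prevent approach and surgeon from becoming aligned, which the model term alone repairs only at a cost in power. The model term prevents the conservatism that stratification brings to a plain t-test.

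The cost is one Castor setting, one degree of freedom, and booking the surgeon before randomisation, which reduces scheduling freedom. The sample size stays at 50 evaluable and 56 recruited. If patients have already been randomised, the model and the table of surgeon by arm can still be adopted before the subsidence data are compared.
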